5.1 Product features

The abdominal aortic stent-graft and delivery system is used for the endovascular treatment of infrarenal abdominal aortic aneurysms. The product uses nitinol wires and polyester films as the basic implant materials and is composed of one body stent and two limb stents. The bare stent, barb, and neck at the proximal end of the body stent are designed to land in the aortic neck to reduce the risk of chronic displacement; The delivery system has an ultra-low profile; the diameter of the outer sheath of the body stent is 14F or 16F, and the diameter of the outer sheath of the limb stents is 12F. The surface has a hydrophilic coating. The stent graft can be introduced percutaneously through the sheath, which reduces the risk of trauma to the access blood vessel. The delivery system has a bare segment main body tip capture mechanism to allow accurate intraoperative positioning and safe and stable operability.

5.2 Structural composition

The abdominal aortic stent-graft and delivery system is composed of the stent-graft and a supporting delivery system. The stent-graft is composed of three modules: body stent-graft, CUFF stent-graft, and branch stent graft, the materials of which include the metal stents, graft, suture, release wire and the marker coil. The structure of the stent-graft is shown in Figure 1 and Figure 3.

The delivery system is used to facilitate the delivery, control and deployment of the stent-graft into the patient, and is mainly composed of the tapered tip, inner tube, multiple lumen tube, outer sheath, grip and other parts. The structure of the delivery system and the assembly position of the stent-graft in the delivery system are shown in Figure 2.

The body stent-graft has 12 marker coils, with 4 marker coils on the bare stent located at the proximal edge of the graft, 1 marker coil located at segment 3 and 5 of one ipsilateral limb respectively, 1 marker coil at segment 1 and 2 of the contralateral limb respectively, and 4 marker coils at the distal end of contralateral limb flush with the distal end of the graft.

The CUFF stent-graft has 6 marker coils, with 4 marker coils at the proximal end flush with the proximal end of the graft, and 2 marker coils at the distal end flush with the distal end of the graft.

The limb stent-graft has 2 marker coils, with 1 marker coil at the proximal end flush with the proximal end of the graft, and 1 marker coil at the distal end flush with the distal end of the graft.

At the proximal end of the outer sheath of the delivery system, there is a radiopaque ring made of platinum iridium alloy. The outer sheath of the delivery system is a non-hydratable catheter.

The specification and dimension of abdominal aortic stent-graft are represented by length L1, L2, L3 and diameter D1, D2 and D3, and its structure is shown in Figure 1. L1 represents the length of the ipsilateral graft of the body stent-graft; L2 represents the graft length of the CUFF stent-graft; L3 represents the graft length of the limb stent-graft; D1 represents the proximal diameter of the body stent-graft, D2 represents the diameter of the CUFF stent-graft, and D3 represents the distal diameter of the limb stent-graft.

[figure not shown]

Figure 1 Structural diagram of the stent-graft

[figure not shown]

Figure 2 Structural diagram of the delivery system and the assembly position of the stent-graft

Refer to Figure 1 for the dimensions and specifications of stent-graft: L1, L2, L3, D1, D2 and D3 should be selected from the dimensions listed in Table 3.

Specification of stent-graft

Name	Diameter (D) mm Tolerance±2	Length (L) mm Tolerance±5
body stent-graft	22、 24、 26、 28、 30、 32、 34 (D1)	90、 100、 110、 120、 130、 140 (L1)
Contralateral limb stent-graft	10、 12、 13、 14、 16、 18、 20、 22、 24 (D3)	80、 90、 100、 110、 120、 130、 140 (L3)
CUFF stent-graft	22、 24、 26、 28、 30、 32、 34、 36 (D2)	40 (L2)

Specifications of delivery system

Name	Optional size		Tolerance
Diameter of the outer sheath (French)	12F(4.0mm) 、 14F(4.7mm)、 16F(5.3mm)		±2F(0.66mm)
Effective length of outer sheath (mm)	14F、 16F	550mm	±50mm
	12F	610mm	

5.3 Working principles and mechanism of action

Through the delivery system, the stent-grafts are deployed into the appropriate lesion site to isolate the aneurysm from the circulatory system and prevent aneurysm rupture. The aneurysmal vessel wall may shrink over time. Intimal cells permeate the pores in the graft material over time and eventually cover the stent-graft completely.

5.4 Scope of study

The study is being conducted in multiple centers in China, alongside a smaller number of centers in Europe, chiefly within vascular surgery departments and in those subjects with a definitive diagnosis of abdominal aortic aneurysm before surgery.

5.5 Risks

Please refer to the Design Failure Mode and Effects Analysis (DFMEA) Report (of Abdominal Aortic Stent-Graft and Delivery System) for details.

6、 Indications, contraindications, and precautions

6.1 Indications:

- Abdominal Aortic Stent-Graft and Delivery System is indicated for the treatment of abdominal aortic aneurysms with a proximal neck length ≥ 15 mm.

6.2 Contraindications:

- Severe stenosis or calcification near the aneurysm, leading to difficulty in achieving apposition of vessel wall and stent graft.
- Difficult access due to severe stenosis or tortuosity in the iliac artery or femoral artery
- Subjects with ruptured aneurysm or acute aneurysm
- Subjects with an infectious aneurysm.
- Those who are allergic to contrast agents or unable to tolerate contrast agents due to renal insufficiency.
- Patients with severe coagulation disorder and/or high risk of postoperative hemorrhage.
- Aneurysmal neck angulation greater than 60°
- Patients with blood supply to vital organs originating from the aneurysmal sac.
- Patients with other comorbidities and whose life expectancy does not exceed one year
- Subjects with connective tissue diseases, such as Marfan syndrome
- Minors and pregnant women
- Subjects who are allergic to nitinol
- Subjects who are considered not suitable for treatment with stent graft.

6.3 Precautions

- Before using the product, physicians must be suitably trained in and have a clear understanding of the principle, clinical application, complications, adverse effects, and hazards of aortic stent graft surgery.
- This product comprises a main body stent-graft and delivery system, a contralateral limb stent-graft and delivery system, and a CUFF stent-graft and delivery system, all of which are packaged separately.

- The Abdominal Aortic Stent-Graft and Delivery System must have been disinfected and sterilized with ethylene oxide prior to release for clinical use.
- This product is for single use only. The company shall assume no liability or responsibility for any cross infection or other adverse consequences caused by reuse of the stent-graft, delivery system or any other component of the product.
- Do not use if the sealed package is found to be damaged.
- Please read the instructions carefully before use.

7、 Overall Design

7.1 Design

7.1.1 Study objectives

The purpose of this study is to observe the clinical outcomes of Minos™ Abdominal Aortic Stent-Graft and Delivery System in the treatment of abdominal aortic aneurysm in a real-world patient population, to assess its effectiveness and the acceptability of the risks inherent in its use, and to identify any new or emerging risks.

7.1.2 Method selection and its justification

Minos™ Abdominal Aortic Stent-Graft and Delivery System was granted a Registration Certificate for Medical Device in the People's Republic of China in March 2019, Registration No.: GXZZ 20193130182, and was CE-Marked in September 2019, Certificate No.: M.2019.106.12584. This post-marketing, real-world clinical trial will be conducted on this basis. The study is designed as a prospective, multi-centre, observational registry study. Following review and approval of the study protocol and patient informed consent form by the relevant local ethics committee, the Internet registration system will be used to register all patients treated with Minos™ Abdominal Aortic Stent-Graft and Delivery System who consent to participation in the registry. The investigators at participating study sites will determine the eligibility of patients for enrollment in the study according to the inclusion criteria. The participants and investigators will sign the Informed Consent Form as confirmation of the patient consenting to participation in the study. All participants will be followed up in accordance with the study protocol until 5 years after implantation.

7.1.3 Measures to avoid and reduce bias

This study will be conducted in multiple centers in and outside of China at the same time. The Internet registration system will be used to register all participants. Clinicians in each study site will select those patients that meet the inclusion criteria to minimize any selection bias created by selection of ineligible patients. Standard operating practices will be adopted to reduce performance bias. Objective index data will be collected as much as possible; design and quality control measures will be strictly investigated, sufficient contact with participants will be maintained as far as possible to maximize the follow-up data obtained and to minimize patients and data lost to follow up during the life of the study. The imaging data obtained from follow-up investigations will be evaluated by blind film reading method as part of the study's data analysis stage. The relevant indicators such as device related adverse events and serious adverse events will be determined by an independent Clinical Event Committee and independent data management and statistical analysis will be utilized to avoid evaluation bias.

7.1.4 Selection of subjects

Inclusion criteria

To be enrolled, patients must meet all the following criteria:

- Diagnosis of infrarenal abdominal aortic aneurysm
- Plan to treat with Minos™ Abdominal Aortic Stent-Graft and Delivery System
- Voluntary participation and completion of Informed Consent Form, with willingness to participate in follow-up to 5 years post-procedure.

Exclusion criteria

- Subjects in whom use of the Minos™ Abdominal Aortic Stent-Graft and Delivery System is contraindicated.

Indications:

- Abdominal Aortic Stent-Graft and Delivery System is indicated for the treatment of abdominal aortic aneurysms with a proximal neck length ≥ 15 mm.
- **Contraindications:**
 - Severe stenosis or calcification near the aneurysm, leading to difficulty in achieving apposition of vessel wall and stent graft.
 - Difficult access due to severe stenosis or tortuosity in the iliac artery or femoral artery
 - Subjects with ruptured aneurysm or acute aneurysm
 - Subjects with an infectious aneurysm.
 - Those who are allergic to contrast agents or unable to tolerate contrast agents due to renal insufficiency.
 - Patients with severe coagulation disorder and/or high risk of postoperative hemorrhage.
 - Aneurysmal neck angulation greater than 60°
 - Patients with blood supply to vital organs originating from the aneurysmal sac.
 - Patients with other comorbidities and whose life expectancy does not exceed one year
 - Subjects with connective tissue diseases, such as Marfan syndrome
 - Minors and pregnant women
 - Subjects who are allergic to nitinol
 - Subjects who are considered not suitable for treatment with stent graft.

Criteria and procedures for termination of the study/treatment

- Should severe safety concerns arise, the study shall be suspended in time.
- If the therapeutic efficacy of the investigational device is found to be poor or ineffective such that it is of no clinical value, the study shall be suspended.
- The discovery of major errors in the clinical trial protocol or significant deviation from it, making it difficult to evaluate the safety and efficacy of the investigational product.
- The sponsor requests suspension (for the reason of funds, management, etc.)
- Revocation is issued by the approving authorities.

Should the above-mentioned situations arise, the sponsor shall promptly inform the investigators, institutions and Ethics Committee of each study center. For subjects who have been treated with the study product, the sponsor shall fulfill the responsibility for the subjects during the study in accordance with the signed Informed Consent Form.

Planned enrollment date

This study is expected to start screening in October 2021, with patients in Europe recruited from early 2024, subject to local ethical committee approval.

Duration of the clinical trial and rationale

After the clinical trial is approved or filed by the Ethics Committee of the participating hospital, it will be registered on “clinicalstudy.gov” or Chinese Clinical trial Registry equivalent. It is expected to take 6 months for the registration, and then the subjects will be screened and enrolled. The expected enrollment period is 24 months, and the follow-up of 30 days, 6 months, 12 months, and 2-5 years will be completed as required. It is expected to take 6 months to summarize and analyze the data and form the statistical report and clinical summary report. Therefore, the overall duration of the clinical trial is anticipated to be approximately 8 years.

Expected duration of each subject's participation

After signing the Informed Consent Form, the subjects will undergo examination as required and imaging follow-up at 30 days, 6 months, 12 months and 2-5 years after surgery in accordance with this protocol. The expected participation time of each subject is 5 years.

Number of subjects required for the clinical trial

It is expected that 200 subjects will participate in this clinical trial.

7.1.5 Primary endpoint

Successful aneurysm treatment: on the basis of technical success and during the follow-up period, the absence of aneurysm rupture, continuous type I and III endoleaks after operation, aneurysm enlargement (aneurysm diameter increased by more than 5mm), secondary intervention due to endoleak, stent occlusion or migration, including open surgery and endovascular surgery. Expected secondary interventions will not be included in the analysis.

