21. SIGNATURE OF STUDY SITES, INVESTIGATORS AND SPONSORS

.....23

Protocol Summary

1、 Objective

To evaluate the clinical outcomes of the Minos™ Abdominal Aortic Stent-Graft and Delivery System in the treatment of Abdominal Aortic Aneurysm in a real-world patient population through a post-market observational registry.

2、 Design

The study is designed as a prospective, multi-centre, post-market, real-world observational registry study. Continuous enrollment is to be conducted for all subjects treated with Minos™ Abdominal Aortic Stent-Graft and Delivery System who meet the inclusion criteria and who voluntarily consent to participate in the study. An enrollment duration period of 24 months is expected for this project and initially, 200 subjects (170 in China and at least 30 in Europe) are to be enrolled. Patient follow up – including CT imaging - will be undertaken in accordance with the usual standard of care at participating sites, and is expected to occur at 30 days, 6 months, 12 months and 2-5 years post-procedure.

3、 Endpoints

1. Primary endpoint

- Technical success rate at 12 months

2. Secondary endpoints

- Incidence of major adverse events at 30 days
- Immediate technical success rate
- Incidence of successful aneurysm treatment at 2-5 years
- All-cause mortality up to 5 years post-procedure
- Aortic aneurysm related mortality up to 5 years post-procedure
- Secondary intervention rates up to 5 years post-procedure
- Aneurysm diameter and variation in aneurysm diameter from 30 days to 5 years post-procedure
- Incidence of type I, III endoleaks from 30 days to 5 years post-procedure
- The incidence rate of stent migration, fracture, stenosis, occlusion and distortion from 30 days to 5 years post-procedure

3. Other endpoints: technical success rate of Hercules balloon and incidence of balloon rupture, where applicable.

4、 Population

Eligible patients will be enrolled according to the inclusion criteria and the exclusion criteria from multiple study sites.

Inclusion criteria

To be enrolled, patients must meet all the following criteria:

- Diagnosis of infrarenal abdominal aortic aneurysm
- Plan to treat with Minos™ Abdominal Aortic Stent-Graft and Delivery System;
- Voluntary participation and completion of Informed Consent Form, with willingness to participate in follow-up to 5 years post-procedure.

Exclusion criteria

- Subjects in whom use of the Minos™ Abdominal Aortic Stent-Graft and Delivery System is contraindicated.

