3.2 Project contents

The study is designed as a prospective, multi-centre, post-market, real-world observational registry study. Continuous enrollment is to be conducted for all subjects treated with Minos™ Abdominal Aortic Stent-Graft and Delivery System who meet the inclusion criteria and who voluntarily consent to participate in the study. An enrollment duration period of 24 months is expected for this project and initially, 200 subjects (170 in China and at least 30 in Europe) are to be enrolled. Patient follow up – including CT imaging - will be undertaken in accordance with the usual standard of care at participating sites, and is expected to occur at 30 days, 6 months, 12 months and 2-5 years post-procedure.

1. Primary endpoint

- Technical success rate at 12 months

2. Secondary endpoints

- Incidence of major adverse events at 30 days
- Immediate technical success rate
- Incidence of successful aneurysm treatment at 2-5 years
- All-cause mortality up to 5 years post-procedure
- Aortic aneurysm related mortality up to 5 years post-procedure
- Secondary intervention rates up to 5 years post-procedure
- Aneurysm diameter and variation in aneurysm diameter from 30 days to 5 years post-procedure
- Incidence of type I, III endoleaks from 30 days to 5 years post-procedure
- The incidence rate of stent migration, fracture, stenosis, occlusion and distortion from 30 days to 5 years post-procedure

3. Other endpoints: technical success rate of Hercules balloon and incidence of balloon rupture, where applicable.

In this study, immediate technical success rate, technical success rate at 12 months, secondary intervention rate, aneurysm diameter and variation in aneurysm diameter, and the incidence of type I and III endoleaks are used as efficacy indicators of the Minos™ Abdominal Aortic Stent-Graft and Delivery System. The incidence of 30-day major adverse events, all-cause mortality, aneurysm related mortality, stent migration, stent fracture, stenosis, occlusion and distortion are used as safety indicators of the Minos™ Abdominal Aortic Stent-Graft and Delivery System.

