7.1.6 Secondary endpoints

30-day major adverse events: events that meet one of the following criteria during the study:

- All-cause mortality: death of any cause occurring within 30 days of procedure.
- Intestinal ischemia: lack of sufficient blood flow in the intestine, requiring intensive drug treatment or surgical/intravascular intervention treatment.
- Myocardial infarction: the increase of one or more cardiac biomarkers (especially troponin) with evidence of myocardial ischemia: ECG changes suggesting new ischemia, or imaging evidence.
- Paraplegia: severe paralysis of lower limbs.
- Kidney failure: GFR < 15ml/min, requiring permanent dialysis, renal transplantation, or death due to renal insufficiency.
- Respiratory failure: pneumonia or respiratory failure requiring ventilator support for more than 24 hours after surgery.
- Stroke: symptoms lasting 24 hours due to cerebrovascular diseases such as hemorrhage, embolism or thrombosis.
- Blood loss > 1000 ml: estimated intra-procedural blood loss > 1000 ml.

Immediate technical success: successful introduction and withdrawal of stent graft and delivery system, with accurate positioning of stent graft, normal stent shape, no distortion, bending, stenosis and occlusion, and no accidental coverage of internal iliac artery or visceral artery.

All-cause mortality: death from any cause.

Aneurysm related death: death caused by rupture of abdominal aortic aneurysm or any operation to treat abdominal aortic aneurysm. All deaths shall be judged by the Clinical Events Committee (CEC) to determine the relevance of aneurysm, instruments or surgery.

Secondary intervention: including open and intracavitary intervention. Open surgery: Open surgery performed at any time to address a failure of endovascular treatment due to failure of stent implantation or placement, complications or other clinical conditions, or after the initial success of endovascular treatment. Secondary endovascular intervention: any intravascular surgical intervention performed to resolve complications such as endoleak, aneurysm expansion, stent occlusion, stent migration and stent defect after the implantation of Minos™ system.

Change in aneurysm diameter: including “enlargement”, which refers to an increase of aneurysm diameter greater than 5mm; “reduction”, which refers to a reduction of aneurysm diameter greater than 5mm; and “stable”, which refers to a change in aneurysm diameter less than or equal to 5mm.

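### The protocol names one primary endpoint (technical success at 12 months, never defined) and defines another (successful aneurysm treatment, with no 12-month time point)

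*Protocol*

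**What the plan says.** The endpoint lists in the Protocol Summary and section 3.2 agree with each other. The primary endpoint is "Technical success rate at 12 months". The secondary endpoints include immediate technical success and, separately, "Incidence of successful aneurysm treatment at 2-5 years". The efficacy indicators in 3.2 include "immediate technical success rate, technical success rate at 12 months, secondary intervention rate" and leave out successful aneurysm treatment.

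Section 7.1.5 carries the heading Primary endpoint, but its only entry is: "Successful aneurysm treatment: on the basis of technical success and during the follow-up period, the absence of aneurysm rupture". The further components are absence of persistent type I and III endoleaks and of "aneurysm enlargement (aneurysm diameter increased by more than 5mm), secondary intervention due to endoleak, stent occlusion or migration". Its time frame is the open one in "on the basis of technical success and during the follow-up period".

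The only definition of technical success for the stent graft is in 7.1.6, among the secondary endpoints: "Immediate technical success: successful introduction and withdrawal of stent graft and delivery system, with accurate positioning of stent graft, normal stent shape". It continues with absence of distortion, bending, stenosis and occlusion, and no unintended coverage of the internal iliac or visceral arteries. (Section 7.1.7 defines technical success for the Hercules balloon, which is a different device.)

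**The concern.** A registry with one primary endpoint should let any two analysts produce the same headline number. Here the name points to one outcome and the definition to another. They cannot be two labels for one thing: 7.1.5 uses technical success as one ingredient of treatment success, and the endpoint lists put the two terms in different tiers at different times.

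Other rules depend on knowing which outcome is primary. Section 8.5 imputes missing values for the primary endpoint and for no other. Section 8.1 admits subjects to the per-protocol set only if the main outcome measures are observable. Section 14 treats failure to assess the primary endpoint as required as a major deviation. Each of these applies to different subjects and different data depending on the reading.

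**Working it through.** This is mainly a comparison of text, so the passages are set side by side first.

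**1. Name against definition**

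| Place | Term used | Tier | Time |
|---|---|---|---|
| Protocol Summary; 3.2 | Technical success | Primary | 12 months |
| Protocol Summary; 3.2 | Immediate technical success | Secondary | Procedure |
| Protocol Summary; 3.2 | Successful aneurysm treatment | Secondary | 2-5 years |
| 7.1.5 | Successful aneurysm treatment | Primary (by heading) | Follow-up, no cut-off |
| 7.1.6 | Immediate technical success | Secondary | Procedure |

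No section defines technical success at 12 months, and none equates it with treatment success.

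**2. Readings the text permits**

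- A: the 7.1.6 outcome as recorded at the procedure.
- B: the stent-shape parts of 7.1.6 (distortion, bending, stenosis, occlusion) read again on 12-month imaging.
- C: the 7.1.5 composite assessed at 12 months.

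**3. How they relate.** If technical success means the 7.1.6 definition, C requires A, so rate(C) ≤ rate(A) in the same patients. This ordering does not carry over to B. A patient with untreated stent stenosis at 12 months and no other event fails B but can pass C. A patient with sac growth above 5 mm around a normally shaped stent passes B and fails C.

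**4. Effect on dependent rules.** Under A, later withdrawal cannot cause a missing primary outcome, so the imputation rule in 8.5 would have nothing to act on. Under B or C it would. Per-protocol membership under 8.1 needs only procedural data under A, but 12-month follow-up under B or C.

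**5. Can the gap be sized?** The protocol gives no expected rate for any reading. Section 8.3 says the 200 subjects do not come from a statistical calculation, so there is no sample-size figure to reproduce. The nearest number is the pre-market 12-month clinical success in section 4, a third label that is also undefined: 121/136 = 88.97%, which agrees with the stated 89%.

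Exact 95% interval, as 8.2 specifies: lower = Beta⁻¹(0.025; x, n−x+1), upper = Beta⁻¹(0.975; x+1, n−x). For 121/136 this gives 82.5% to 93.7%.

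Illustration at n = 200. The 89% is borrowed from that study, and the other three rates are assumptions for reading A:

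| Assumed rate | Count | Exact 95% CI | Difference from 89% |
|---|---|---|---|
| 89% | 178/200 | 83.8% to 93.0% | – |
| 95% | 190/200 | 91.0% to 97.6% | 6 points |
| 98% | 196/200 | 95.0% to 99.5% | 9 points |
| 99% | 198/200 | 96.4% to 99.9% | 10 points |

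The 89% is itself uncertain as a stand-in for C. The pre-market study had 136 − 121 = 15 failures and 10 deaths by 12 months, and 7.1.5 has no death component. If all 10 deaths had been counted as failures for that reason alone (not stated), the rate without them would be 131/136 = 96.3%. The differences from 98% and 99% would then be 1.7 and 2.7 points. The gap therefore depends on the assumptions, and the documents do not fix it.

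**The case against.** The best defence is that the intent can be guessed. Section 7.1.5 can be read as a generic definition whose time points come from the endpoint lists. Section 8.5 expects withdrawals to cause missing primary data, which fits a follow-up outcome. Section 8.3 says the study is descriptive, with no comparison or formal test, so no pass/fail decision depends on the choice, and immediate technical success is reported in any case. Much of this stands: the open time frame in 7.1.5 is sensible if the lists supply the time points, and the lack of a hypothesis limits the damage. But the lists supply 12 months for a different term, and nothing in 8.5 separates the composite from a 12-month stent-geometry reading.

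Three stronger readings go too far.

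- A reader might infer that 12-month technical success must equal immediate technical success because the definition is purely procedural. Stent shape, distortion, stenosis and occlusion can change after the operation, and the protocol follows stenosis, occlusion and distortion from 30 days to 5 years.
- A reader might infer a gap of 8 to 11 points, beyond sampling error, by setting 89% against technical success of 97-100%. The latter has no source in the protocol and the former is an undefined outcome. The exact intervals at 89% and at an assumed 95% overlap, and comparing separate intervals is the wrong test for nested outcomes in the same patients.
- A reader might infer that the sponsor will choose the reading after seeing results. Section 8.4 does plan analyses at 30 days and 6 months, before the 12-month one, so the text leaves room for this. Nothing shows that it is intended, and an analysis plan not at hand may settle which outcome is reported. It would still not reconcile a protocol that disagrees with itself.

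**Conclusion.** The contradiction is real and should be corrected. The protocol's only primary endpoint has a name without a definition and a definition under another name, and following the text can give three different primary results. This conclusion rests on the wording alone and needs no numerical assumption. The direction is known for one pair only: the composite cannot exceed immediate technical success, provided the precondition in 7.1.5 means the 7.1.6 definition. The size of the difference cannot be computed from the documents; the figures above are illustrations. The practical consequence is that the headline result, the primary-only imputation in 8.5 and the per-protocol set in 8.1 are not determined.

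**What to change.** Use one primary endpoint term with one time point in the Protocol Summary, in both the endpoint list and the efficacy-indicator list of section 3.2, and in 7.1.5. Successful aneurysm treatment at 12 months is the best fit: it keeps the 7.1.5 definition, the 12-month time in the lists and the 2-5 year secondary series.

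In 7.1.5, replace the time phrase at the end of "on the basis of technical success and during the follow-up period" with *from the index procedure through the assessment time point*. State that this time point is 12 months for the primary endpoint and each of 2, 3, 4 and 5 years for the secondary endpoint. Do not write a fixed 12-month cut-off into 7.1.5: it holds the only definition of treatment success, and a fixed cut-off would leave the 2-5 year endpoint undefined.

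Keep technical success for the procedure-day secondary endpoint only. If the sponsor does want technical success at 12 months, it must define it explicitly.

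The cost is a protocol amendment. Section 12.2 requires written ethics approval for revisions, and the after-the-fact notice allowed in 12.1 and 14 covers only non-substantive changes unrelated to the endpoint. Sites in both China and Europe are affected. The 12-month visit, imaging and adverse-event evaluation are already scheduled, so data collection and the 200 subjects are unchanged.
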